**Table 1: Physiological Parameter Maximums allowed During Walking Activities**

BP	Systole: 200 mmHg; Diastole: 110 mmHg or increase $> 10$ mmHg; or pulse pressure narrowing $> 10$ mmHg
HR	60-80% of HR reserve: $\text{resting HR} + (208 - 0.7 \times \text{age} - \text{resting HR}) \times [60-80\%]$
RPE	$> 15$ on a 20-point scale

Surveys, questionnaires, and clinical tests/measures may be collected either on paper documents, or electronically by direct entry into a secure REDCap server. REDCap links for surveys/questionnaires may be sent to the participant via email, allowing the participant to respond to the survey questions directly. Hard copies will be scanned and uploaded to a secure Sharepoint folder or to REDCap.

\*\*\* Note that all study procedures will be conducted in accordance with site-specific COVID-19 protocols corresponding to the research site at which the visits are completed. For example, study procedures performed at the Neuromotor Recovery Laboratory will follow the guidelines outlined in the NRL Return to Research Plan submitted to Boston University in response to COVID-19. Similarly, visits performed at Harvard University will follow Harvard's approved procedures, and visits performed at Spaulding Rehabilitation Hospital will follow the SRH guidelines. Please see

Appendix XVIII for the approved COVID-19 laboratory operating procedures for each research site. For research sites other than Boston University, the BU research team will ask for and retain a record of the site's approval to recruit and enroll research participants. An example set of guidelines may include the following (from the NRL Return to Research Plan for visits performed at Boston University): Participants will be required to wear a surgical mask throughout the study visit and should not remove the mask at any time unless drinking water or absolutely necessary. All researchers present at the visit will wear surgical masks throughout the visit. If a researcher or physical therapist must come into close proximity (< 6 feet) of the participant, such as during guarding or placement of sensors, that researcher will don appropriate personal protective equipment (PPE), which includes gloves, gown, and goggles or face shield in addition to the surgical mask. Throughout the visit, researchers and physical therapists will minimize number of people interacting with the participant and time spent in close proximity to the participant, as is outlined in the Return to Research Plan. Given the unpredictability of COVID-19 policies that may change regularly with short notice, if this guidance changes at any point, the research team will follow the most recent guidance provided. \*\*\*

**Figure 1:** Enrollment and study flow for participants testing at Boston University (BU), Harvard University (HU), and Spaulding Rehabilitation Hospital (SRH).

### **Study Visit Workflow:**

#### **a. Primary Screening (1 visit; over the phone or in-person at Boston University, Harvard University, or Spaulding Rehabilitation Hospital)**

The first contact with an interested participant will take place over phone (**up to 10-15 minutes**). If the potential participant is already at Boston University, Harvard University, or Spaulding Rehabilitation Hospital (e.g. currently participating in a research study or clinical care), the participant may opt to perform the primary screen in-person. This primary screening does not count toward the total number of sessions. During the primary screening, the study will be explained in detail, and any questions that the participant has will be answered. If the participant maintains interest in participating in the study, he/she will be asked the questions from the primary screening form to determine consideration for the study.

- Case-specific information useful to the physical therapist or trained investigator's assessment of each participant may also be collected. This information includes knowledge of any serious comorbidities or medical conditions that may affect participation in the study, general walking ability, and prior experience with electrical stimulation. The collected information will help physical therapists and the research team to confirm eligibility and to better prepare for subsequent study visits.
- **Note on participants previously known to Boston University through participation or screening in other studies at Boston University:** Participants who have recently participated or have been screened for other studies at Boston University may be contacted to determine their interest in participating in this research study. We will only contact participants who have expressed interest and given permission to be contacted for additional research studies at Boston University. If the participant agrees to participate, information already known to Boston University may be used to complete the primary and/or secondary screening documentation. Study staff may reach out to participants to fill in any gaps and update information as needed on a case-by-case basis. Participants who are actively involved in other studies that have potential effects on walking performance will be eligible for consideration in Phase 1 and 2 of this study and will not be eligible for Phase 3 until after completion of the other study.
- **Note on participants known to Boston University through participation or screening in studies with a collaborating institution:** Participants who have recently participated or have been screened for a research study at one of our collaborating institutions may be referred to us via a collaborator. If the participant agrees to participate in our study, information already known to our collaborators may be shared with Boston University to complete the primary and/or secondary screening documentation. Study staff may reach out to participants to fill in any gaps and update information as needed on a case-by-case basis. This may include identifiable data such as screening forms, medical history, and study data.

If the individual is deemed eligible for Group 1 or Group 2, they will be scheduled for a secondary screening visit to confirm eligibility and review the Informed Consent Form.

If the individual is deemed eligible for the Healthy group, they will be able to review the study's Informed Consent Form with the study team member at the end of this primary screening visit.

### ***Informed Consent:***

For the participant's convenience, the Informed Consent Form and HIPAA Authorization Form, if applicable, can be completed either in person (at this visit or at the beginning of the next visit) or remotely (online, by mail, or using BU Zoom). If remote consenting is preferred, participants can choose one of the following options:

1. Secure eConsent - Participants may sign the Informed Consent Form and HIPAA Authorization Form via REDCap (via eConsent framework) or to print and sign/date the emailed consent form, which will be returned to the study staff by email. Consent forms signed in REDCap will automatically be stored securely in the REDCap File Repository. A version of the signed/dated eConsent form will be provided to the participant by direct download, email, or as a hardcopy at their first in-person visit (participant preference).

2. Zoom/Phone - The researcher will email the consent form and HIPAA authorization to the participant and will review the documents with the participant over phone call or BU Zoom video call. The participant can electronically sign the documents or print the forms, sign them, then scan and email them back to the research team.
3. Mail - Participants may request a paper copy of the consent form and HIPAA authorization by mail which will include a pre-stamped, pre-paid return envelope. They should read and sign the forms and mail them back to the research team.

The participant will be able to check a box on the Informed Consent Form to indicate whether or not they agree to having photo/video taken during study visits.

If the individual is not deemed eligible at the end of the primary screening visit, they will not be able to participate in the study. Any data collected will be de-identified and may be used as part of a baseline cross-sectional dataset (e.g., to characterize individuals' baseline function, or identify characteristics of individuals who were versus were not eligible for the study).

**b. Secondary Screening (1 visit; *in-person at Boston University, Harvard University, or Spaulding Rehabilitation Hospital*)**

The purpose of this visit is to confirm study eligibility and collect clinical measurements that can be used to characterize participants who have had a stroke and to help place them in the appropriate testing group if they are eligible for the study.

This visit will last **up to 3 hours**. Participants who have had a stroke will be asked to complete a medical history and physical examination to assess neurological complications and medical comorbidities, stroke-specific weakness/balance impairment, cognitive or behavioral issues, and communication issues. For example, participants will be asked to complete the following:

- a. NIHSS Cognitive Screen (only Question 1b and 1c)
- b. Medical History
- c. Walking and range of motion assessments (Functional Gait Assessment, Fugl-Meyer)
- d. Assessments to understand participant's physical activity and comfort performing various tasks (Activities-Specific Balance Confidence scale, International Physical Activity Questionnaire (IPAQ))
- e. Overground comfortable walking speed (CWS) and fast walking speed (FWS) assessed using three 10-meter walk tests for each speed
- f. Overground long-distance walking ability using the 6-minute walk test
- g. Brief, harnessed, treadmill walking

We may also collect sensor data (e.g. movement-related) and/or vitals (e.g. heart rate and blood pressure) during the visit.

If the individual is deemed eligible, they will review and sign the study's Informed Consent Form and a HIPAA Authorization Form that allows their physician to disclose protected health information for research purposes, which is necessary to obtain medical clearance and communicate with the physician's office during the course of the study, if necessary. Procedures for reviewing and signing these forms are described under the primary screening visit in Section L, Part (a).

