## **SECTION I: PARTICIPANT POPULATION**

**Provide the Number of Participants to be Enrolled. If you have sub-groups or more than one arm, please separate out these enrollment numbers. Note:** Please account for participants who may drop out or be withdrawn from the study. Anyone who signs a consent form is considered to be enrolled in the research regardless of whether they complete any study procedures.

This study has a target enrollment of up to 40 participants who have had a stroke and 40 participants who have not had a stroke. Participants with post-stroke hemiparesis will participate in the patient-in-the-loop development of a novel neuroprosthesis that harnesses the power of electricity to exploit the residual force generating capacity of post-stroke muscles during functional activities. These participants may be enrolled into one of two groups (depending on whether they are in an active rehabilitation program) and may participate in as many of the three phases of this study (listed below) as they wish. Healthy participants will also participate in the patient-in-the-loop development of this novel neuroprosthesis and will be enrolled into a healthy participant group. Healthy participants may partake in device development and testing phases of this study. Regardless of participant group or research phase, the target enrollment for the entire study across all approved research sites will not exceed a total of 80 participants. Participants who complete screening at one research site will complete subsequent testing at the same location, or at the testing site that is most convenient for that participant. Participants may switch study sites if they wish, however all visits for a particular sub-study (e.g. a clinical training study in Phase 3) must be conducted at the same site.

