### Eligibility Criteria

#### Inclusion Criteria (Healthy):

- Age 18-80 years old
- No known, self-reported neuromotor disorder, gait pathology, or comorbidity that would interfere with participation (musculoskeletal, cardiovascular, neurological, skin, and vasculature conditions)

Inclusion Criteria (Stroke):

- Age 18-80 years old
- Diagnosis of a stroke
- Observable gait deficits (confirmed at secondary screening visit)
- Independent ambulation (with or without an assistive device) for at least 30 meters (confirmed at secondary screening visit)
- Full range of motion in ankle (confirmed at secondary screening visit)
- Ability to follow a 3-step command (confirmed at secondary screening visit)
- Resting heart rate between 40-100 bpm (confirmed at secondary screening visit)
- Resting blood pressure between 90/60 and 170/90 mmHg (confirmed at secondary screening visit)
- Provide HIPAA Authorization to allow communication with healthcare provider as needed during the study period
- Medical clearance by a physician

Additional Inclusion Criteria (Group 1: active rehabilitation):

- Currently undergoing active rehabilitation (independent of research procedures for this study) under the guidance of a therapist/physiatrist.

Additional Inclusion Criteria (Group 2: no active rehabilitation):

- Not currently receiving active rehabilitation (independent of research procedures for this study) under the guidance of a therapist/physiatrist.

Exclusion Criteria (Healthy):

*Note: Exclusion criteria are the specific criteria which would disqualify an individual from participating in the study, not simply the opposite of the inclusion criteria.*

- Diagnosed or self-reported neuromotor disorder or gait pathology
- Serious co-morbidities that may interfere with ability to participate in this research (musculoskeletal, cardiovascular, neurological, skin, and vasculature conditions)

Exclusion Criteria (Stroke):

*Note: Exclusion criteria are the specific criteria which would disqualify an individual from participating in the study, not simply the opposite of the inclusion criteria.*

- History of lower extremity joint replacement (i.e. hip, knee, ankle)
- Severe aphasia and/or speech/language disorder, limiting ability to express needs and comprehend instructions
- Shows signs of neglect or hemianopia
- Serious comorbidities that may interfere with ability to participate in the research (e.g. musculoskeletal, cardiovascular, pulmonary)

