Trained study personnel will conduct the visit. First, the informed consent document will be reviewed in detail with the participant. All procedures will be explained, and voluntary participation will be confirmed with signed consent prior to the initiation of data collection. Study participants will be asked to confirm their preference on the collection of photo/video during testing via a check-off box on the consent form. Photo and video refer to the audiovisual media taken primarily of the participant's lower body during walking with or without the reNeu device. Photo/video will not contain identifiable information, such as participant names, and will be stored on an encrypted and password-protected SharePoint folder accessible only by the research team. If any photo/video captures a participant's face or other identifiable landmark, that area will be blurred out if used for publications, presentations, training purposes, or

promotional purposes. Photo/video may also be used for visual assessment and correlation with other biomechanical outcome measures obtained during data collection.

Consent to participate in the study is obtained during the secondary screening visit, along with the participant's HIPAA authorization. After HIPAA authorization is obtained, the research team will put together a medical clearance packet to send to the participant's primary care physician. This packet includes the following:

- a. Medical clearance form (Appendix IV)
- b. HIPAA authorization form with participant's signature
- c. Cover sheet asking physician to review and sign in the notes section

Once the packet is prepared, it will be faxed to the primary care physician for the physician's signature. Once this clearance is obtained, the participant may begin testing visit procedures described in Section L, Part (d).

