***Medical Clearance:***

We will seek medical clearance for qualifying individuals who are eligible for Group 1 or Group 2 based on the primary and secondary screening visits. Medical Clearance will be sought annually from the individual's primary healthcare provider (i.e., primary care physician, neurologist, cardiologist, nurse practitioner, or physician assistant) as indicated on the HIPAA Authorization Form. This process is described in the Medical Clearance Standard Operating Procedure (Appendix XI).

Individuals who are eligible for the Healthy group who self-report a medical condition that might pose a risk to participation in this research study will be excluded.

\*\*\* Note: Participants who were enrolled, screened, and medically cleared while this study was approved under the Harvard IRB (Harvard IRB19-0878) are permitted to forgo conducting those same procedures before conducting further study procedures under this protocol. Since the process of obtaining medical clearance and the procedures conducted during screening and subsequent research visits has not been altered from the original protocol under the Harvard IRB, this will not affect data integrity or subject safety and willingness to participate in the study. The research team will send a note to the primary physicians of enrolled participants to notify them of this change and provide them an opportunity to contact us with any questions or concerns. The note will let physicians know that 1) the protocol has transferred from Harvard to Boston University, 2) the research team, goals, procedures, and risks remain the same, and 3) they can contact the research team at any time if they have questions or concerns. \*\*\*

If the individual is not deemed eligible at the end of this secondary screening visit, they will not be able to participate in the study. Any data collected will be de-identified and may be used as part of a baseline cross-sectional dataset (e.g., to characterize individuals' baseline function, or identify characteristics of individuals who were versus were not eligible for the study).

***c. Subsequent Screening (over the phone or in-person before subsequent study visits at Boston University, Harvard University, or Spaulding Rehabilitation Hospital)***

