### **Describe the plan to minimize risks. Include in the description the availability of any medical or psychological resources.**

The PI and co-investigators have extensive experience with clinical research involving individuals poststroke. Many of the investigators have a clinical background in physical therapy and many study personnel and students have training in CPR and first aid. All of the aforementioned risks will also be mitigated through the following:

- Potential participants will be provided with the consent form and be provided ample time to read it and ask questions. The research team will address any concerns. Participants will be told that participation in the study is completely voluntary and they have the right to withdraw from the study at any time.
- Adequate rest periods and water will be provided to optimize comfort and reduce fatigue.

- Total walking time per session will be limited to one hour.
- Trained investigators will monitor vital signs and check for symptoms of distress at each study visit. Procedures will be halted as physiologic signs clinically warrant activity cessation. Any findings out of the ordinary will be reported to the participant's primary healthcare provider, concluding the study visit procedures.
- Trained investigators will use overhead harness when possible. Treadmill and over-ground walking tests will be completed with overhead harnessing to prevent a fall. There might be situations where harnessing is not possible such as when transitioning between activities or when harness is not available, when testing activities occurring outside of the lab in the hallway, or when harnessing is not clinically necessary (e.g. training progression to reduce reliance on external balance support to improve balance during walking). During these situations when harness is not used, an investigator will provide close guarding and will use a gait belt if indicated.
- Trained investigators will ensure that participants are safe to walk without their usual brace (e.g. ankle foot orthosis). The determination will be based on clinical assessment of participant's gait, such that the participant would be able to walk without high risk for toe catches, tripping, or ankle instability (e.g. ankle rolling).
- For poststroke participants, we will obtain medical clearance from their primary healthcare provider prior to enrollment in the study.

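### Protocol Section L(b) makes the consent signature depend on screening results, against Section K's consent-first rule, and data from ineligible people who may never have signed can be used

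*Protocol*

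**What the plan says.** **Consent at secondary screening.** Section L(b) lists the visit's content first: history, Functional Gait Assessment, Fugl-Meyer, questionnaires, three 10-meter walks at each of two speeds, a 6-minute walk and a brief harnessed treadmill walk, with sensor data and vitals optional. After the list it states: "If the individual is deemed eligible, they will review and sign" the consent form and a HIPAA authorization. Section K covers the same visit. It puts review of the consent document first and says that "voluntary participation will be confirmed with signed consent prior to the initiation of data collection".

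**Where else signing may happen.** The Informed Consent text under Section L(a) lets the forms be completed at that visit, at the start of the following one, or remotely. Section L(b) refers back to it for the signing procedure.

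**People found ineligible.** For those who fail secondary screening, Section L says: "Any data collected will be de-identified and may be used as part of a baseline cross-sectional dataset". The same provision appears for those who fail primary screening.

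**Medical clearance.** Section M says that for stroke participants "we will obtain medical clearance from their primary healthcare provider prior to enrollment in the study". The instruction note in Section I says: "Anyone who signs a consent form is considered to be enrolled in the research".

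**The concern.** Two sections give different orders for the same visit. A site that follows Section L(b) literally would run research walking tests on people who have not signed. Section M itself recognizes that mobility testing carries a risk of falls. A site that follows Section K would not do this. The plan does not say which section governs.

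The second issue is the data. If signing comes only after a favorable eligibility decision, those who fail have not signed, yet their measurements may be kept for a research dataset. Removing identifiers afterwards does not meet Section K's rule, which concerns signature before collection. What is at stake is participants' rights and the standing of that dataset, rather than any effect estimate.

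**Working it through.** No arithmetic applies. The check sets the sections side by side.

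**1. The two orders**

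| Step | Section K | Section L(b) |
|---|---|---|
| 1 | Primary screen | Primary screen |
| 2 | Consent reviewed and signed at secondary screening; HIPAA authorization at the same visit | Secondary-screening assessments and walking tests |
| 3 | Data collection | Eligibility decision |
| 4 | Medical clearance | Consent and HIPAA authorization signed |
| 5 | Part (d) research visits | Medical clearance |
| 6 | – | Part (d) research visits |

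The orders differ on consent relative to the screening tests. They agree that clearance follows signing and precedes the Part (d) visits.

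**2. Can eligibility be decided without testing?** No. Section I marks six stroke criteria as confirmed at the secondary visit: gait deficits, 30-meter independent ambulation, ankle range of motion, following a 3-step command, resting heart rate and resting blood pressure. The first two require watching the person walk. No criterion refers to the 6-minute walk, the fast walks or the treadmill. Under Section L(b), what precedes the signature is therefore at least the assessments behind those six criteria and at most everything on the list; the text does not say where in the list the decision falls. Section L(b) also gives characterizing participants as a purpose of the visit, so this is data collection in Section K's sense as well as an eligibility check.

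**3. Does Section L(a) settle the order?** It allows a signature before the tests but does not oblige anyone to obtain one. The end of L(a) lets eligible Healthy candidates review the form at the primary screen, and sends stroke candidates to the secondary visit both to confirm eligibility and to review it. The conditional sentence in L(b) is then the only statement of order in the account of that visit.

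**4. Who could be in the dataset without a signature?**
- Primary-screen failures: Section K obtains consent at the secondary visit, and L(a) takes forward only those found eligible. These people would ordinarily not have signed under either order.
- Secondary-screen failures: signed under Section K, not signed under Section L(b).

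Section K ticks only the written consent form for adults. Neither the waiver of documentation (Box 1) nor the waiver or alteration of consent (Box 2) is completed.

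**5. Clearance, enrollment and testing.** The Section K clearance packet contains the signed HIPAA form, obtained together with consent. If enrollment means signing (Section I note), clearance comes after enrollment, contrary to Section M. If it means placement in a group after both screenings (the Study Visit Procedures overview in Section L), there is no conflict. That overview also puts clearance and consent before testing without saying whether screening tests count, whereas Section K ties clearance to Part (d) testing visits. Clearance is itself a stroke inclusion criterion in Section I, yet the Medical Clearance text seeks it for people already called eligible.

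**The case against.** The best defense is that this is one loosely worded sentence. The L(a) text on signing at the start of the next visit, read where it stands, most naturally means the start of secondary screening for a stroke candidate, which agrees with Section K. Section K also offers a remote consent route, and the Section L overview puts consent before testing. This stands in part: Section L does not uniformly place the tests before consent, and early signing is allowed. It does not remove the conflict, because L(b) states a condition on signing and nothing in Section L requires the early route.

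A reader might go further and infer that walking tests before medical clearance contradict Sections K and M. The documents do not support that. Section K makes clearance a condition for Part (d) visits only, and Section M places it before enrollment without mentioning screening tests. A reader might also conclude that Section M's promise is impossible to keep. That follows only from the Section I definition, which sits in the form's instruction for counting participants; under the group-level meaning it can be kept.

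It is also fair to say that neither Section K nor Section M speaks directly about ineligible people's data. That point is derived from Section K's rule on signature before data collection. The consent form was not available for this review, so what it says about screening data could not be checked.

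**Conclusion.** The concern holds in limited form. Section L(b) ties the signature to a decision that needs assessments at the same visit, and this conflicts with Section K. Section L also permits research use of data from people who may never have signed, with no waiver completed.

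The population exposed to the ambiguity is the stroke target of up to 40, plus people who are screened and never sign, whose number is not given. It would be tempting to say that up to 3 hours of testing precede signature, or that every ineligible person is in the dataset unsigned. Neither follows. Three hours is the ceiling for the whole visit, including history and questionnaires, and no duration is given for the tests. Use of the data is permitted, not stated to occur, and some people could have signed early. Others may not repeat screening, because existing information can complete the forms and those screened under the previous IRB approval are exempt.

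No SAP analysis is affected. The SAP reports ten completers, all with written consent and medical clearance, without timing, and none of its comparisons uses the baseline cross-sectional dataset. The inconsistent use of enrollment and testing around clearance is a separate drafting point. The conclusion assumes that the L(b) sentence is read as written.

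**What to change.** - Amend Section L(a) and L(b) so that consent and HIPAA authorization are signed before any secondary-screening test, as Section K already has it for consent, and remove the condition on eligibility.
- In both places where Section L covers ineligible people's data, limit the baseline cross-sectional dataset to people who signed, or state the IRB-approved basis for using others' data. This matters most for primary-screen failures, whom reordering the secondary visit does not reach.
- For data already collected, compare each consent date and time with the screening-test record before anything enters that dataset.
- Define enrollment and testing once and reconcile Sections I, K, L and M on medical clearance. How clearance relates to the screening tests is for the sponsor and the IRB to decide.

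The cost is a text amendment and a revised visit checklist. Consent discussions will be held with some people who then fail screening. If the Section I definition is kept, those people count as enrolled, so the target of up to 40 should be checked against the expected number of screen failures.
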